11.3 Procedure for Recording and Reporting Adverse Device Effects

All SAEs and all possibly device related AE/ADEs will be collected from first application of the study treatment products at the baseline visit until study exit.

Beginning with the first study treatment, the investigator will determine whether any SAEs or possibly device related adverse experiences have occurred by evaluating the subject's signs, symptoms, and other test results or assessments.

All SAEs and possibly device related AEs / complications and ADEs (expected or unexpected) which occur during the specified study period, whether observed by the investigator or by the subject, and whether or not thought to be related to treatment product or to study procedures, will be reported in detail on the appropriate CRF and followed until resolution, stabilization, or death, according to Good Clinical Practice (GCP). The record of the SAE/ADE will include a description of the event, start date, stop date, duration, outcome, intensity, if it was serious, relationship to treatment product or study procedure (i.e., causality), change in dosage or discontinuation of treatment product, if treatment was required and if the subject died. The investigator must verify this information.

11.4 Procedures for Reporting a Serious Adverse Event/Unanticipated Adverse Device Effect

It is the responsibility of the Investigators to inform their IRB about serious adverse events or other events as required by their IRB procedures and in compliance with the applicable regulations.

The investigator should inform SinuSys either by phone or email, within 24 hours of the investigator becoming aware of the event. SAE/UADEs shall be initially reported to:

Name: [name]
Title: Director, Preclinical and Clinical Development
Address: SinuSys Corp, [name]
[contact]
Email: [contact]

A full investigation of any SAE/UADE will be conducted by the Investigator in collaboration with SinuSys Corporation. The Investigator shall report the results of such evaluation to the IRB within 10 working days after notice of the effect. Only Unanticipated possibly device related complications will need to be considered for possible reporting to the FDA. Please consult with regulatory counsel for guidance.

If principal investigator determines that an SAE/UADE presents an unreasonable risk to subjects, the investigation must be terminated as soon as possible, but no later than 5 working days after the investigator makes this determination.

All subjects with an SAE/UADE must be followed up and the outcomes reported. The Investigator should supply SinuSys Corporation and the IRB with any additional requested information (e.g., hospital discharge summary, autopsy report, pathology report, operative report, terminal medical report, etc).

12 STATISTICAL PLAN

12.1 Sample Size

Up to approximately 50 subjects will be enrolled into the study. This study is designed to evaluate basic device usability and confirm safety and effectiveness of Restora Nasal Spacer.

There is no success criteria set based on statistical calculation.

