1 PROTOCOL SYNOPSIS

Title: Rates of MM synechiae formation post ESS: a double-blind randomized controlled study comparing Silastic and the Restora™ steroid eluting MM spacer

Primary Objective:

This study is designed to evaluate basic device usability and confirm safety and effectiveness of the Restora™ Steroid eluting spacer as compared to a Silastic spacer.

Background/ Rationale:

Endoscopic sinus surgery (ESS) is the gold standard surgical intervention for chronic rhinosinusitis that is not adequately controlled with maximal medical therapy.

In some patients, underlying inflammation (discharge, edema and polyposis), compounded by inflammation caused by surgical trauma may lead to an uncontrolled healing response, which results in the synechiae formation in the middle meatus (MM).

Incidence of synechiae formation varies in literature and ranges between 4-35%. Presence of middle meatal synechiae can impair sinus drainage, promote sinusitis, and limit endoscopic visualization of the sinus cavities postoperatively. This may result in difficulty in performing postoperative routine endoscopic debridement and examination, which is paramount to a successful outcome from ESS. Spacers are often inserted during surgery between nasal mucosal surfaces to prevent synechiae.

The aim of this study is to see if a steroid-impregnated spacer is more effective at reducing inflammation after sinus surgery than a Silastic spacer.

Study Population: Patient suffering from chronic rhinosinusitis in need of ESS

Number of Centers: 2-3

Number of Subjects:

A total of 49 patients will be treated.

Test article:

Restora Spacer material loaded with Mometasone Furoate

Study Design:

This is a double-blind randomized controlled study of 49 patients with chronic rhinosinusitis that require ESS.

Screening

In the screening period, inclusion/exclusion criteria for the study participation will be checked. Subjects who satisfy these criteria will be invited to participate in the study. Their consent will be recorded. As a standard of

care, all patients will fill out the validated SNOT-22 quality of life outcome questionnaire at this pre-op visit.

Blinding

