8 STUDY DESIGN AND ENDPOINTS

Approximately 50 patients will receive spacers during their ESS procedures and be followed for 90 days. This will require enrolling approximately 60 patients between all of the participating centers to account for possible loss-to-follow-up (LTf).

- **Primary Endpoint**
 - 35-day sinonasal mucosal inflammation assessed by rigid endoscopy and graded on Lund-Kennedy sinus mucosal endoscopic staging system
- **Secondary Endpoints**
 - 90-day post ESS incidence of middle meatal synechiae
 - 35 and 90-day sinonasal mucosal inflammation assessed by rigid endoscopy and graded on Lund-Kennedy sinus mucosal endoscopic staging system
 - 35 and 90-day intraocular pressure (IOP) assessed using applanation tonometry and compared to baseline IOP obtained preoperatively
 - 35 and 90-day post-ESS incidence of middle meatal synechiae
 - 90-day validated Sinonasal Outcomes Test-22 (SNOT- 22) scores
 - 35-day frequency of postoperative interventions, including lyses of adhesions and debridement.
 - 35-day frequency of oral steroid rescue
 - 35 days middle turbinate position

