10 RISK/BENEFIT ASSESSMENT

10.1 Potential Risks

There are two potential sources of risks that can be derived from the use of the Restora spacer: 1) due to the spacer material and shape and 2) due to the drug loaded onto the spacer.

The risks associated with the spacer material itself is considered minimal as the material is biocompatible for its intended use and the material shape (thickness, and area) is similar to that of the standard Silastic Silicone sheet that is used surgically.

The risk associated with the drug is comparable to that with the use of the commercially available Intersect Propel stent, as the amount of drug loaded on Restora™ is equivalent to that loaded onto Propel Stent, 370 μ gm. In addition, the anti-inflammatory steroid, Mometasone Furoate (active ingredient in Nasonex) has been approved for intra-nasal delivery since 1997. The recommended daily dose delivered for treatment of allergies is 2 sprays per nostril per day and for polyposis is 2 sprays per nostril twice a day. Each spray dose is 50 μ g. Therefore, the total maximum recommended dose for the spray user is 400 μ g per day and total of 2,800 μ g over a 7 day period. Compared with this recommended dose, the dose of Mometasone Furoate delivered by Restora is at least 7 fold less than that for the Nasonex.

The potential risks of study participation fall into the following categories:

Frequent: expected to occur in more than 25% of people (more than 25 out of 100 people)

Probable: expected to occur in 10-25% of people (10-25 out of 100 people)

Occasional: expected to occur in 1-10% of people (1-10 out of 100 people)

Remote: expected to occur in less than 1% of people (less than 1 out of 100 people)

Incredible: expected to occur in less than 0.1% of people (less than 1 out of 1000 people).

The risks and possible side effects may include the following:

1. Device Risks

- Premature Displacement of spacer post placement – Remote
- Swallowing of spacer – Incredible
- Adherence of crusting to the implant, resulting in or contributing to sensation of pain/pressure/headache - Occasional
- Foreign body response, including formation of granulation tissue - Remote
- Choking- Incredible

2. Drug Risks

- Nasal irritation and burning - Remote
- Intranasal bleeding - Remote
- Localized infection (bacterial, fungal, or viral) in the nose or pharynx – Occasional
- Nasal Dryness - Incredible
- Glaucoma/elevation of intraocular pressure - Incredible

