10.2 Potential Benefits of Study Participation

There may be no direct benefits of study participation. However, subjects will undergo an enhanced level of clinical scrutiny compared to routine clinical care, which may provide some indirect health benefits.

In addition, there could be a benefit of using a drug-eluting spacer post ESS to decrease rate of synechiae formation, and frequency of postoperative interventions, including lyses of adhesions and debridement.

This study is intended to confirm the feasibility of the use of the Restora Nasal Spacer for this purpose.

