12.3 Statistical Analyses

Appropriate statistical methods will be used to analyze the data. Descriptive statistics for continuous variables will consist of the mean, median, standard deviation, minimum, and maximum values. For categorical variables, the number and percentage of each category will be displayed.

For the primary endpoints the following acceptance criteria had been defined:

- Safety: The study will be considered successful if no Unanticipated Device Adverse Effect occurs during device residence time and the overall rate of device related complications is clinically acceptable.
- Performance: The study will be considered successful if there is a trend or significant difference in primary end point between Restora and Silastic spacer

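### Zero UADEs in about 49 patients plus an unquantified complication judgement cannot support the aim of confirming safety: 0/49 leaves an exact upper limit of 7.3% (two-sided 95%)

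*Combined protocol and SAP*

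**What the plan says.** The aim is given in section 12.1: "This study is designed to evaluate basic device usability and confirm safety and effectiveness of Restora Nasal Spacer". The synopsis (section 1), the end of section 4.1 and section 6 say the same in nearly the same terms. Section 12.1 and the synopsis add that no success criterion rests on a statistical calculation.

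Section 12.3 nevertheless sets acceptance criteria. The study succeeds on safety if "no Unanticipated Device Adverse Effect occurs during device residence time" and if the overall rate of device-related complications is clinically acceptable. No figure, comparator or procedure defines acceptable. The section lists means, medians, standard deviations and ranges for continuous variables, and numbers and percentages for categorical ones. It names no interval and no rate to be excluded.

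The size is stated in three ways:
- Synopsis: "A total of 49 patients will be treated".
- Section 8: "Approximately 50 patients will receive spacers during their ESS procedures and be followed for 90 days", and "This will require enrolling approximately 60 patients between all of the participating centers".
- Section 12.1: "Up to approximately 50 subjects will be enrolled into the study".

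**The concern.** A zero count in a small trial is weak evidence about a rare event, and its strength depends wholly on the number of patients. The plan turns such a count into a declared success and describes the purpose as confirmation, but never says which event rates the result would rule out. The second condition does not supply the missing assurance, because with no threshold any observed rate can be judged acceptable after the data are seen.

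At stake is the safety conclusion itself. Followed as written, the plan lets the report say that safety was confirmed when the data are still compatible with a serious unanticipated effect in several patients per hundred.

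**Working it through.** **Inputs.** The number treated is 49 (synopsis), with 50 and 60 as variants (sections 8 and 12.1). Each treated patient receives one Restora and one Silastic spacer (section 8.7), so every treated patient counts in the Restora denominator. The success count is zero UADEs (section 12.3). The documents give no confidence level, sidedness or safety margin, so 95% is an assumption and both sidednesses are shown. The plan has no figure of its own to reproduce.

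**Step 1: what zero events excludes.** With 0 events in n patients, the exact (Clopper-Pearson) upper limit is 1 − a^(1/n), with a = 0.05 for one-sided 95% and a = 0.025 for two-sided 95%. For n = 49:
- one-sided: 1 − 0.05^(1/49) = 5.93%
- two-sided: 1 − 0.025^(1/49) = 7.25%
- rough check by the rule of three: 3/49 = 6.12%, close to the one-sided figure

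**Step 2: how often the zero-UADE condition is met.** The probability of no events is (1 − p)^n at a true rate p.

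| n | Upper limit, one-sided | Upper limit, two-sided | p = 1% | p = 2% | p = 3% | p = 5% |
|---|---|---|---|---|---|---|
| 49 | 5.9% | 7.3% | 61.1% | 37.2% | 22.5% | 8.1% |
| 50 | 5.8% | 7.1% | 60.5% | 36.4% | 21.8% | 7.7% |
| 60 | 4.9% | 6.0% | 54.7% | 29.8% | 16.1% | 4.6% |

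The row for 60 applies only if all enrolled patients were treated. Section 8 reads more naturally as about 60 enrolled so that about 50 are followed.

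**Step 3: where zero becomes the likelier result.** Setting (1 − p)^49 = 0.5 gives p = 1 − 0.5^(1/49) = 1.4%. Zero events is more likely than not only below that rate.

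**Step 4: scale.** With zero events, excluding a rate of 5% needs 59 patients (one-sided) or 72 (two-sided). Excluding 1% needs 299 or 368.

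**Step 5: earlier experience.** Section 7.2 reports 23 earlier Restora patients with no adverse events. Pooling gives 0/72, with upper limits of 4.1% (one-sided) and 5.0% (two-sided). Pooling is also doubtful: those spacers released 64.81 µg on average, whereas loading is now adjusted to target up to 370 µg, and 370/64.81 = 5.7 times as much.

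**The case against.** The strongest defence is that sections 1 and 12.1 disclaim any statistically based success criterion. The plan claims to exclude no particular rate, so this may be only a loosely worded aim. It stands that there is no wrong calculation here. It does not dispose of the point, because section 12.3 goes on to define success on safety, and that declaration is what a report would carry.

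A second defence is that the safety evidence is wider than the UADE count. Section 11.3 collects all serious events and possibly device-related events to study exit, intraocular pressure is measured at 35 and 90 days, and section 12.3 promises appropriate methods, which does not rule out intervals. All true. But the zero-UADE condition covers residence only, about 6 to 8 days, so the scheduled pressure readings fall outside it. Whatever the wider data show enters the rule only through the complication condition, which has no threshold.

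Four stronger readings are tempting, and the documents do not support them:
- *That zero UADEs alone means success.* Section 12.3 joins it to the complication condition, and both must be met.
- *That a 6% or 7% limit contradicts section 10.1.* Of the 19 risks graded there, 16 are classed below 1% (4 Remote, 12 Incredible). These are anticipated risks graded one by one, and most are minor. A UADE under section 11.1 is a serious effect not previously identified in nature, severity or degree of incidence. No expected UADE rate is stated, so the classes are no benchmark for this limit. No section uses a zero count to support them.
- *That zero events is likely even for a device with a rate the protocol would find alarming.* The protocol names no such rate, and at 2% or more zero is the less likely result.
- *That section 10.2 concedes the safety aim is only feasibility.* The sentence reads "This study is intended to confirm the feasibility of the use of the Restora Nasal Spacer for this purpose". The purpose it refers to is the benefit just described, fewer synechiae and postoperative interventions, not safety.

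**Conclusion.** The point holds as an overstated safety aim with no statement of precision. The only objective part of the safety rule is a zero count. In 49 patients, that count excludes only UADE rates above 5.9% (one-sided 95%) or 7.3% (two-sided 95%). Across the sizes the documents give, the limit runs from 4.9% to 5.9% one-sided and from 6.0% to 7.3% two-sided, so the inconsistent sample size does not alter the conclusion. The plan should be changed on this point: the trial can run as designed, but its safety conclusion would claim more than its size can show.

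This rests on a 95% level, which is assumed, on patients being independent, and on all treated patients being observed through residence. Fewer observed patients would raise the limit.

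**What to change.** In section 12.3, report the counts of UADEs, serious adverse events and device-related complications with exact (Clopper-Pearson) two-sided 95% limits, computed on the actual Safety population rather than a fixed 49. State beside the safety criterion that zero events in about 49 to 50 patients excludes only rates above about 7% (two-sided). Use the two-sided figure in text and table alike so that they agree.

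In sections 1, 6 and 12.1, and in the matching sentence of 4.1, replace the wording about confirming safety with, for example: provide a preliminary estimate of the rates of UADEs and device-related complications. Word the safety conclusion by the upper limit. If the complication condition stays as a success criterion, say before data lock how it will be judged. The documents give no basis for a figure, and none is proposed here.

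No extra patients, visits or data are needed. The cost is wording and one column in the safety table. The downside for the sponsor is a less favourable headline claim.

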12.2 Analysis Populations

The following subject populations will be created:

Safety (Safety): All subjects enrolled who underwent the device placement procedure, regardless of outcome.

Intent To Treat (ITT): All subjects enrolled who underwent the device placement attempt, regardless of outcome.

Per Protocol (PP): A subset of the ITT population that excludes subjects with major protocol deviations (to be identified prior to data lock).

The primary efficacy analysis will be carried out on both ITT and PP populations.

No effort will be made to impute or extrapolate data to replace missing values.

12.3 Statistical Analyses

Appropriate statistical methods will be used to analyze the data. Descriptive statistics for continuous variables will consist of the mean, median, standard deviation, minimum, and maximum values. For categorical variables, the number and percentage of each category will be displayed.

For the primary endpoints the following acceptance criteria had been defined:

- Safety: The study will be considered successful if no Unanticipated Device Adverse Effect occurs during device residence time and the overall rate of device related complications is clinically acceptable.
- Performance: The study will be considered successful if there is a trend or significant difference in primary end point between Restora and Silastic spacer

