The study will be double-blinded. Each patient will be his or her own control. The Silastic spacer will be placed on one side and the steroid-eluting spacer will be placed on the other. Neither the patient nor the assessor will know on which side the respective spacer is placed. The PI at the primary site will be the blinded assessor.

Procedure and follow up

Patient will undergo ESS and the spacers will be placed in the operating room upon procedure completion. Subjects will return to clinic after 6-8 days to have the spacers removed. The removed spacer materials will be shipped to SinuSys for residual steroid content analysis. After the initial visit, patients are seen again in clinic at 35 and 90 days postoperatively. At each visit endoscopic videos will be collected to enable scoring, as detailed in the endpoint section below. As a standard of care all patients are treated with oral antibiotics (Clavulin or Clindamycin if allergic to Penicillin) while they have spacers inserted into their nose.

The detailed study schedule is provided in Appendix A.

Projected Study Timelines

Anticipated Total Study Duration: Enrollment – 1-2 months, Follow up 3 months.

Study Endpoints

- **Primary Endpoint**
 - 35 day sinonasal mucosal inflammation assessed by rigid endoscopy and graded on Lund-Kennedy sinus mucosal endoscopic staging system
- **Secondary Endpoints**
 - 90-day sinonasal mucosal inflammation assessed by rigid endoscopy and graded on Lund-Kennedy sinus mucosal endoscopic staging system
 - 35 and 90-day intraocular pressure (IOP) assessed using applanation tonometry and compared to baseline IOP obtained preoperatively
 - 35 and 90-day post ESS incidence of middle meatal synechiae
 - 90-day Sinonasal Outcomes Test-22 (SNOT- 22) scores
 - 35-day frequency of postoperative interventions, including lyses of adhesions and debridement.
 - 35-day frequency of oral steroid rescue
 - 35 days middle turbinate position

Inclusion Criteria

- 1) Age between 18 and 75 years
- 2) Diagnosis of chronic rhinosinusitis (CRS), per current guidelines
- 3) Patients who need to undergo primary bilateral complete endoscopic sinus surgery
- 4) Subject has the ability to follow the study instructions, is willing to be available on the specific required study visit days, and is willing to complete all study visit procedures and assessments

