8.7 Treatment visit

Patients will undergo bilateral ESS procedure. Each patient will receive one Silastic and one Restora spacer, placed bilaterally.

As a standard of care all patients are treated with oral antibiotics (clavulin or clindamycin if allergic to penicillin) while they have spacers inserted into their nose.

The device(s) can be removed anytime upon the subjects' request or if the Investigator deems it necessary.

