11 ADVERSE EVENTS / COMPLICATIONS

11.1 Serious Adverse Event (SAE)/Unanticipated Adverse Device Effect (UADE) Definition

Serious Adverse Event (SAE): A SAE is defined as any untoward medical occurrence that:

- Results in death,
- Is life-threatening,
- Requires inpatient hospitalization or prolongation of existing hospitalization
- Results in medical or surgical intervention to prevent life threatening illness
- Results in injury or permanent impairment to a body structure or a body function
- Results in persistent or significant disability/incapacity

Also in the category of SAE is:

- Any other unanticipated serious problem caused by or associated with the device that relates to the rights, safety, or welfare of subjects [21 CFR 812.3(s)]

Important medical events that may not result in death, be life-threatening, or require hospitalization may be considered a SAE when, based upon appropriate medical judgment, they may jeopardize the subject or may require medical or surgical intervention to prevent one of the outcomes listed above. Elective hospital admission will not be considered an SAE for this study.

Unanticipated Adverse Device Effect (UADE) is any serious adverse effect on health or safety, any life-threatening problem or death caused by, or associated with a device, if that effect, problem, or death was not previously identified in nature, severity, or degree of incidence in the application; or any other unanticipated serious problem associated with a device that relates to the rights, safety, or welfare of subjects.

All SAE/UADEs will be collected from first application of the treatment product at the baseline visit until study exit.

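### The zero-UADE safety criterion stops at spacer removal (planned day 6-8), so a UADE starting later cannot fail it, although UADEs are collected to study exit at about day 90

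*Combined protocol and SAP*

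**What the plan says.** The safety rule is in section 12.3. The study succeeds on safety if "no Unanticipated Device Adverse Effect occurs during device residence time and the overall rate of device related complications is clinically acceptable". The two conditions are joined, so both must be met. The first is tied to the time the device is in place. The second has no time window and no numerical limit.

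Residence is short. The synopsis states: "Subjects will return to clinic after 6-8 days to have the spacers removed". Appendix A gives the same window (day 6 plus up to 2 days). Section 8.7 allows a shorter stay: "The device(s) can be removed anytime", on the subject's request or the investigator's judgement.

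Collection is much longer. Section 11.1 states: "All SAE/UADEs will be collected from first application of the treatment product at the baseline visit until study exit". Section 11.3 applies the same period to serious adverse events (SAEs) and possibly device-related events. The last visit is at 90 days (section 8.8), or 13±2 weeks in Appendix A.

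The UADE definition in 11.1 sets no limit on onset. A serious device-associated effect qualifies "if that effect, problem, or death was not previously identified in nature, severity, or degree of incidence in the application".

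**The concern.** The objective in section 6 includes confirming safety, and the zero-UADE condition is the only part of the safety rule that can be applied without a judgement call. Its window covers less than a tenth of the period over which the same events are collected, and no section explains why. As written, the study could be declared a safety success with a UADE on record that began after the spacers came out.

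The gap lies in the success rule only. Section 11.4 still requires late UADEs to be investigated and reported, and intraocular pressure (IOP) is still compared with baseline at 35 and 90 days as a secondary endpoint.

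A smaller inconsistency affects the records behind the safety assessment. The note under the unrelated category in 11.2 says such events need not go into the CRFs. Section 11.3 says SAEs, "whether or not thought to be related to treatment product or to study procedures, will be reported in detail on the appropriate CRF". The two conflict for an SAE judged unrelated.

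**Working it through.** The plan gives no figure to reproduce: section 12.1 says that no success criterion rests on a statistical calculation. The check compares the windows and then counts days and visits.

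**Windows**

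| Item | Start | End | Source |
|---|---|---|---|
| Zero-UADE condition | placement | removal, day 6-8 or earlier | 12.3; synopsis; 8.7; Appendix A |
| Complication-rate condition | not stated | not stated | 12.3 |
| UADE collection | first application | study exit, about day 90 | 11.1; 8.8 |
| Exit visit window | day 77 | day 105 | Appendix A, 13±2 weeks (11×7 and 15×7) |

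Section 12.3 swaps two words of the term defined in 11.1; I read them as the same term.

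**Share of follow-up after the criterion closes** = (exit day − removal day) / exit day

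- Exit day 90, removal day 8: (90 − 8)/90 = 82/90 = 91.1%
- Exit day 90, removal day 6: (90 − 6)/90 = 84/90 = 93.3%
- Exit day 77, removal day 8: 69/77 = 89.6%
- Exit day 105, removal day 6: 99/105 = 94.3%

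Earlier removal raises these shares.

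**Scheduled assessments (Appendix A)**

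- Adverse events/UADE: treatment, removal, 5 weeks, 13 weeks. Two of the four come after removal.
- IOP: screening, 5±1 weeks (days 28-42), 13±2 weeks (days 77-105). Neither post-baseline reading falls in days 0-8.

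The IOP timing should not be over-read. Section 10.1 lists "Glaucoma/elevation of intraocular pressure" in its rarest category (under 0.1%), so a raised pressure would be a UADE only if it were serious and went beyond what was already identified.

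**Onset or detection.** The rule turns on when an event occurs, which I take as onset. Section 11.3 states: "The record of the SAE/ADE will include a description of the event, start date, stop date". A UADE that began during residence but was found later would therefore still count. Only onset after removal escapes.

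**Illustration.** The documents give no UADE rate or timing, so the inputs here are assumptions. Let p be a subject's UADE risk to day 90 and f the share of the cumulative hazard that falls during residence. With 49 treated subjects (synopsis), the chance that the zero-UADE condition fails is 1 − (1 − p)^(49f) as written and 1 − (1 − p)^49 if it ran to exit.

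| p | constant hazard, f = 6/90 to 8/90 | f = 0.8 | to exit |
|---|---|---|---|
| 1% | 3.2-4.3% | 32.6% | 38.9% |
| 2% | 6.4-8.4% | 54.7% | 62.8% |
| 5% | 15.4-20.0% | 86.6% | 91.9% |

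At f = 1 the two windows give the same answer. The effect of the restriction thus runs from nil to large, depending on onset timing that nobody has documented.

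**The case against.** The strongest reply is that the short window is deliberate. Section 4.1 says the steroid elutes while the spacer is retained, so the criterion matches the period of exposure, and a collection period longer than a criterion period is not in itself a contradiction. The last point is true, but no section gives this rationale. The plan also schedules IOP and UADE assessments at 5 and 13 weeks, so it treats effects after removal as worth looking for. Section 7.2 reports no adverse events in 23 earlier patients. Those spacers released 64.81 µg on average, against a target here of up to 370 µg, and the section does not say how long the patients were followed after removal.

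The second reply is that the complication-rate condition catches late events. A UADE is device-associated by definition, so a late one naturally belongs in that rate. That stands, and it narrows the consequence: success with a late UADE on record also requires someone to judge the overall rate acceptable. With no threshold and no named judge, however, that condition does not force failure.

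Third, 11.4 requires the investigation to be terminated if the principal investigator finds an unreasonable risk, whatever the timing. That also stands, and it protects subjects. It does not alter what the success rule would conclude.

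Finally, the recording conflict between 11.2 and 11.3 has no bearing on the window, since an unrelated event is not a UADE. That is correct; it is a separate, minor repair.

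**Conclusion.** The concern holds. The zero-UADE condition closes at removal, and no other section extends it or justifies the shorter window. At the nominal exit, 91-93% of follow-up days fall outside it (90-94% across the exit visit window).

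The conclusion rests on reading the rule by onset date and on removal at day 6-8. It does not rest on the binomial illustration, and the share of days is not a share of risk. It should not be widened to say that late UADEs are ignored: they are collected, investigated and reported, and may be weighed in the complication rate. The change should be made, but it is a modest one.

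**What to change.** 1. In 12.3, reword the first safety condition as: *no UADE (as defined in 11.1) occurs from spacer placement to study exit*.
2. Report device-related complications over the same period as a count and percentage with an exact 95% confidence interval, by subject and by device, because each subject carries both spacers. The window repair does not depend on this, but the interval shows how little a clean result can exclude: zero events in 49 subjects leaves a two-sided upper limit of 1 − 0.025^(1/49) = 7.3%.
3. In 11.2, limit the note to non-serious unrelated events and add that all SAEs are recorded regardless of relationship, to agree with 11.3.

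The cost is two wording changes and one interval, submitted to the IRB as section 14 requires. No new visits or data are needed. The downside is a slightly stricter criterion, since a UADE starting after removal would now fail it. The missing threshold in the complication-rate condition is a separate defect that these changes do not cure.
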